1. DULCET STUDY PROTOCOL SYNOPSIS

Title:	Dulcet Study: A non-significant risk clinical investigation of the VibratoSleeve, a therapeutic ultrasound (TUS) phased array, for patients with ischemic and neuroischemic diabetic foot ulcers (DFU).
Design:	Prospective, single arm, open label clinical trial to evaluate the feasibility of TUS in the treatment of DFU, with three different treatment levels Low, medium and high acoustic intensities, corresponding to different peak negative pressures)
Device Name and Intended Use:	VibratoSleeve is an array of single element ultrasound transducers, driven in a phased manner, and held in place externally by an adjustable sleeve. In this study, device experts will use the VibratoSleeve in a clinic setting and will evaluate for evidence of an increase in distal limb TcPO ₂ in adult subjects with ischemic and neuroischemic DFU.
Visit Schedule:	Visits will occur at screening (baseline data) and at three in-clinic treatment sessions, each separated by at least a 1-week interval.
Study Objectives:	The objectives of this study are: 
 Establish a safety profile for both the procedure and the VibratoSleeve TUS for the treatment DFU. Gather initial evidence of the treatment and immediate post-treatment efficacy of the VibratoSleeve TUS in DFU subjects. Request subject usability feedback: comfort, tolerability, and human factors of the VibratoSleeve assessed by questionnaire and certain human and operator factors associated with the use of the device.
Number of Subjects and Defined Point of Enrollment	Up to twelve subjects will be required for treatment and evaluation. The defined point of enrollment will be the time at which the patient signs the Informed Consent Form (ICF) to undergo screening procedures to ascertain eligibility. An estimated 50% of enrolled subjects may not satisfy all inclusion/exclusion criteria. Therefore, up to twenty-four subjects may have to be enrolled to generate twelve evaluable subjects qualified for both treatment and evaluation.
Inclusion Criteria	
 Presence of at least one DFU (grade 0 or 1 according to the University of Texas classification). Diagnosis of diabetes mellitus. Diagnosis of PAD that meets at least one of the following conditions: 
 Ankle-brachial index (ABI) of < 0.9 in the same limb as the DFU Toe Brachial Index (TBI) ≤ 0.6 OR Toe Blood Pressure ≤ 50 mmHg Documented history of PAD for a minimum of 3 calendar months prior to time of enrollment Aged ≥ 22 years
Exclusion Criteria	
 Rutherford 6 stage PAD. Active DFU infection. End-stage renal disease on dialysis.

	
 4. HbA1c > 11%. 5. Planned PAD revascularization. 6. Prior stenting in posterior tibial, anterior tibial or peroneal artery. 7. Re-vascularization procedure within 30 days prior to enrollment in the study. 8. History or diagnosis of severe chronic venous insufficiency or mixed arterio-venous disease. 9. Acute limb ischemia within 30 days prior to treatment. 10. History or diagnosis of deep venous thrombosis below the knee in treatment leg. 11. Any conditions that, in the opinion of the investigator, may render the patient unable to complete the study or lead to difficulties for patient compliance with study requirements, or could confound study data. 12. Patient's enrollment in another investigational drug or device study that has not completed the required primary endpoint follow-up period.
Safety Endpoint	To evaluate the overall safety of the VibratoSleeve TUS device for the treatment of PAD, the Principal Investigator will undertake a detailed assessment of all procedure- and/or therapy-related adverse events.
Efficacy Endpoints	
 • Transcutaneous Oxygen Pressure (TcPO₂). • Perfusion rate, as measured with the FlowMet device (Medtronic). • DFU tissue oxygenation (StO₂) and hemoglobin content (HbT2), as measured with the Clarifi device (Modulim).
Treatment	
Each TUS treatment will be provided at a clinic following debridement and ulcerated wound assessment. Each subject will receive three levels of TUS treatment (low, medium, and high acoustic intensities, corresponding to different peak negative pressures). Each of the three treatments will occur on separate dates, spaced at least one week apart. The duration of each treatment level will be 90-minutes.
 
The VibratoSleeve will be applied to the posterior calf (proximal to the TUS) using water-based acoustic coupling gel by trained clinical trial staff, and TUS delivered using Vibrato's custom generator. This study is designed to address acute changes in perfusion with each of the three TUS treatments.

Statistical Hypothesis	Statistical hypotheses will not be applied in this pilot study. Information collected during the study may be used to support a 510(k) application as well as to select the endpoints and determine sample sizes for future trials.
Study Duration	The Sponsor expects the trial to last eight months from the time the first subject enrolls until the time of the last follow-up visit.

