2. STUDY FLOW CHART

3. SCHEDULE OF EVENTS

Table 1. Data collection requirements

Activity	Screening / Baseline (Day 0)	1 st Treatment Session (Days 0+)	2 nd Treatment Session (1 st Treatment + ≥7 Days)	3 rd Final Treatment Session (2 nd Treatment + ≥7 Days)
Informed Consent	X			
Demographics & Medical Drug History	X			
Clinical Evaluation & Rutherford and University of Texas Classification and Calf Circumference (mm)	X			
I/E Criteria	X			
ABI/TBI	X*	X	X	X
Transcutaneous Oxygen Pressure (TcPO ₂)		X	X	X
Perfusion of the foot: FlowMet and Clarifi devices		X	X	X
Vital Signs		X	X	X
Subject Questionnaire		X	X	X
Adverse Events	X	X	X	X
Protocol Deviations	X	X	X	X

*Only required if needed for PAD documentation (see inclusion criteria #3)

All treatment visits will be completed within 3 months of the first treatment session

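### The Visit Schedule and Table 1 list no adverse-event check after the day of the third treatment session, although sessions 1 and 2 are each followed by one at least 7 days later

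*Protocol*

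**What the plan says.** The Visit Schedule in the Protocol synopsis gives the full list of visits: "Visits will occur at screening (baseline data) and at three in-clinic treatment sessions, each separated by at least a 1-week interval". Table 1 in section 3 (Schedule of Events) has matching columns: screening, a first session, "2 nd Treatment Session (1 st Treatment + ≥7 Days") and "3 rd Final Treatment Session (2 nd Treatment + ≥7 Days"). The adverse-event row is ticked in all four columns, and there is no fifth column.

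Study Duration in the synopsis counts the length of the trial "until the time of the last follow-up visit". No follow-up visit appears in the Visit Schedule or in Table 1.

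The first-listed objective is to "Establish a safety profile for both the procedure and the VibratoSleeve TUS for the treatment DFU". The Safety Endpoint asks for assessment of every adverse event related to procedure or therapy and sets no time limit. Under Treatment, "Each subject will receive three levels of TUS treatment", one per session, for up to twelve treated subjects. The order of the levels is not stated.

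**The concern.** Adverse-event enquiry is tied to treatment visits, so the check that follows a session exists only because another session comes after it. The last session has no successor. An event that appears after that day has no scheduled point at which anyone asks about it, while the same event after session 1 or 2 would be asked about at the next visit.

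This bears on the first-listed objective. Ascertainment is unequal across sessions, and each session carries a different intensity. An event that is never asked about and never volunteered cannot be recovered by any analysis plan. When enquiry takes place is fixed by the visit schedule, so this belongs in the protocol.

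**Working it through.** **Inputs.** Up to 12 treated subjects (synopsis, Number of Subjects); 3 sessions each (synopsis, Treatment); at least 7 days between consecutive sessions (Visit Schedule and Table 1); adverse-event checks at screening and at sessions 1, 2 and 3 (Table 1).

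**The plan's own figure.** The synopsis derives one number, the enrolment ceiling: 12 / (1 − 0.50) = 24, which reproduces. It plays no part below; the 24 that follows is a count of sessions.

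**Later checks by session, as scheduled.**

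| Session | Later scheduled checks | Minimum days to the next check | Minimum days to the last check |
|---|---|---|---|
| 1 | 2 (sessions 2 and 3) | 7 | 7 + 7 = 14 |
| 2 | 1 (session 3) | 7 | 7 |
| 3 | 0 | none | 0 (same day) |

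The last column gives lengths of ascertainment. Time after sessions 1 and 2 also contains later exposures, so it cannot be read as risk belonging to one intensity.

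**Subject-sessions if all complete.** Total: 12 × 3 = 36. With a later scheduled check: 12 × 2 = 24. Without: 12 × 1 = 12, and 12/36 = 33.3%.

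**Early stopping.** Assume that a subject who stops treatment attends no further visits; the document does not say. Each treated subject then has exactly one session, the last received, with no later check. For n treated subjects the share is n divided by the total number of sessions received. That total is at most 3n, so the share is at least n/3n = 1/3. A subject who stops after session 1 contributes 1 of 1 uncovered sessions, and one who stops after session 2 contributes 1 of 2. For example, if one of the 12 stops after session 1, there are 11 × 3 + 1 = 34 sessions, and 12/34 = 35.3% have no later check.

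**With one contact at least 7 days after the last session, all completing.** Later checks become 3, 2 and 1. Minimum days to the last check become 14 + 7 = 21, 7 + 7 = 14 and 7. Every session then has at least one later check.

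**Same-day capture.** Table 1 ticks adverse events at each treatment session, so all 36 sessions are covered on the day itself. The count above concerns later events only.

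**The case against.** The case for leaving the schedule alone has four parts.

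- **The wording.** The phrase in Study Duration sits in a planning sentence about calendar time and may simply mean the last study visit. The flow chart in section 2 is not shown and may contain a follow-up step. Both points stand, so a reader should not infer that a planned visit was dropped. The gap does not depend on that phrase, however. It rests on the Visit Schedule and Table 1, which are both present and agree with each other.
- **The aim.** The study is a non-significant-risk pilot without hypotheses, and the synopsis says: "This study is designed to address acute changes in perfusion with each of the three TUS treatments". That sentence is about perfusion. It explains why no later efficacy measurement is planned, but it does not confine the safety objective to the treatment day.
- **Spontaneous reports.** The Safety Endpoint has no cut-off, so a later event that a subject volunteers is not excluded. This stands and limits the claim. What is missing is scheduled enquiry after the last session, which the other sessions have.
- **The 7 days.** The protocol gives 7 days as spacing between treatments and nowhere as a safety window. This also stands. The figure serves only to make ascertainment comparable across sessions.

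It is tempting to go further and say that the safety comparison is biased in favour of one intensity. That would follow only if the levels were given in a fixed order. Under that assumption, the level given third would have a later check in 0 of 12 subjects, against 12 of 12 for each of the others. The order is not stated, so the document does not support the inference. If the order varies, the uncovered sessions are spread over the levels, but their number is unchanged.

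**Conclusion.** The point holds as a gap in scheduled, active ascertainment of adverse events after each subject's last session. Its size is 12 of 36 subject-sessions (one third) if all 12 subjects complete three sessions. It is more than one third if any stop early and are not seen again.

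A reader might also infer that the trial has no means of learning of later events, or that the schedule breaks a stated follow-up requirement. Neither is supported: spontaneous reports remain possible, and the protocol sets no window for delayed events. Separately, Study Duration does not match the Visit Schedule and Table 1, and this needs reconciling even if the wording is merely loose.

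The conclusion assumes that the flow chart shows no follow-up step. If it does show one, the problem becomes a mismatch between the chart and the Visit Schedule and Table 1. Confidence is moderate for that reason. The point is worth fixing because safety comes first among the objectives and the remedy is cheap.

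**What to change.** Reconcile Study Duration, the Visit Schedule and Table 1:

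- Add one remote (telephone) adverse-event contact after the last session each subject receives, including subjects who stop early. A contact tied to session 3 would miss those subjects.
- Let the sponsor set the interval, no shorter than the existing 7-day session spacing. Describe it as a data-collection interval and not as a clinical safety window.
- State that adverse-event collection runs from screening through that contact, and make the end point in Study Duration match.
- If the flow chart already shows a follow-up step, bring the Visit Schedule and Table 1 into line with it instead.

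**Cost.** At most 12 calls, about one more week per subject at the 7-day minimum, one new column in Table 1, and a reworded sentence in each of Visit Schedule and Study Duration. No clinic visit or procedure is added. The note under Table 1, "All treatment visits will be completed within 3 months of the first treatment session", covers treatment visits only and need not change. The drawback is that a telephone report is not an examination.

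### Is a ceiling of 24 enrolled subjects too low to deliver twelve evaluable subjects at the protocol's own 50% screen-failure rate?

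*Protocol*

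**What the plan says.** All the figures stand in the Synopsis (Section 1), in the row on number of subjects and point of enrollment. The size is given as "Up to twelve subjects will be required for treatment and evaluation". Enrollment is counted from consent: "The defined point of enrollment will be the time at which the patient signs the Informed Consent Form (ICF) to undergo screening procedures". Screen failures therefore count towards the enrolled total. The failure rate is given as "An estimated 50% of enrolled subjects may not satisfy all inclusion/exclusion criteria", and the row concludes that "up to twenty-four subjects may have to be enrolled to generate twelve evaluable subjects qualified for both treatment and evaluation".

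Two other rows of the Synopsis bear on the point. Under Treatment, each subject receives three intensities: "Each of the three treatments will occur on separate dates, spaced at least one week apart". Under Statistical Hypothesis: "Statistical hypotheses will not be applied in this pilot study". The note to the Schedule of Events (Section 3) requires all treatment visits to fall within 3 months of the first.

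**The concern.** Twelve divided by one half is the mean requirement, yet the sentence presents the result as an upper limit. A limit set at the mean is missed nearly as often as it is met. Screen failures use up the limit, so the sponsor appears to face close to even odds of ending below twelve or having to go above 24.

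The 50% also covers eligibility failure only, while the yield is described as evaluable subjects. Each subject is to attend three sessions on separate dates, so anyone who qualifies and then misses a session seems to come off a total with no reserve. At stake would be the number of subjects who contribute to the within-subject comparison of the three intensities.

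**Working it through.** **Inputs from the Synopsis.** Twelve subjects, worded as a maximum; 50% estimated failure; 24 enrolled, counted from consent; three sessions. No dropout rate, alpha, power, effect size or SD is stated.

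**The plan's own figure.** 12 / (1 − 0.5) = 24. It reproduces exactly.

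**Chance of reaching twelve.** Let X be the number qualifying among 24, binomial with p = 0.5, treating subjects as independent. The mean is 24 × 0.5 = 12 and the SD is √(24 × 0.5 × 0.5) = 2.4.

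| Qualifiers | Probability |
|---|---|
| at least 12 | 58.1% |
| at least 11 | 72.9% |
| at least 10 | 84.6% |
| at least 9 | 92.4% |

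The shortfall probability is 100 − 58.1 = 41.9%. Of this, 92.4 − 58.1 = 34.3 percentage points are outcomes with nine to eleven qualifiers. If recruitment stops at twelve, the mean of min(X, 12) is 11.0.

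**Dependence on the 50%.** With 24 consents, the chance of at least twelve qualifiers is 88.6% at a failure rate of 40%, 75.8% at 45%, 58.1% at 50% and 38.5% at 55%. The 58% therefore holds only if 50% is an exact central rate. If it is a cautious estimate, the chance is higher.

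**Session loss (assumed rates of 10% and 20%; the protocol gives none).** If every qualifier among the 24 could be treated, the chance of at least twelve completers would be 38% or 21%, with means 24 × 0.5 × 0.9 = 10.8 and 24 × 0.5 × 0.8 = 9.6. The protocol treats at most twelve, so these figures do not describe this trial. Under the cap:

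- Mean completers: 11.03 × 0.9 = 9.9, or 11.03 × 0.8 = 8.8.
- Twelve completers require twelve qualifiers and no loss: 0.581 × 0.9^12 = 0.581 × 0.282 = 16%, or 0.581 × 0.8^12 = 0.581 × 0.069 = 4%.

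Under that cap no higher enrollment ceiling offsets session loss. Even with twelve certain qualifiers, all twelve complete with probability 0.9^12 = 28% or 0.8^12 = 7%. Ceilings of 34 or 39, which give a 90% chance of twelve completers without the cap, work only by treating more than twelve.

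**What evaluable means here.** The phrase in the Synopsis speaks of subjects qualified for treatment and evaluation, following directly on a sentence about eligibility. Nothing in the protocol makes completion of all three sessions a condition of being evaluable. The definition of an analysis set and the handling of missed sessions commonly belong to the SAP, which is not at hand. Exclusion criterion 11 already removes patients whom the investigator judges unlikely to complete. The 3 months are an outer limit: two gaps of at least 7 days allow the third session 14 days after the first.

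**What depends on twelve.** No hypothesis is tested and no precision target or minimum size is stated. Nine, ten or eleven subjects comply with the wording.

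**The case for a change.** The best case for the concern is that the protocol itself states the limit and its reasoning, so this is not detail left to the SAP. The derivation is introduced as a consequence of the 50%, and on that figure the limit misses its stated yield about 42% of the time. The Synopsis adds that the data may support a 510(k) application and help size later trials, and one subject is 1/12 = 8.3% of the maximum. The wording could be repaired in two sentences.

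Much of this stands as description. The 58% is exact under its assumptions, 24 is a mean, and the 50% leaves nothing over for loss after eligibility. A ceiling of 28 or 31 would raise the chance of twelve qualifiers to 82.8% or 92.5%.

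It does not follow that the plan is wrong. Dividing by one minus the failure rate is the ordinary planning inflation, and how much margin to add is a choice. No passage says that going above 24 would require an amendment. A missed session reduces the number in the comparisons it affects; it does not undo the design.

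**Conclusion.** The concern does not hold. The protocol's arithmetic is right, and its wording (an estimated rate, subjects who may fail, numbers that may have to be enrolled, up to twelve treated) does not promise twelve. On an exact 50% rate and independent subjects, the likely shortfall before any session loss is one to three subjects, with an average of 11.0 qualifying under the cap of twelve. In a pilot without hypothesis tests or a stated minimum, that misses no size, power or precision the protocol claims. The loss argument rests on assumed rates and on a definition of evaluable that the document does not contain. What remains is a preference for calling 24 an expectation and for defining evaluable, and neither would alter a result or a conclusion.

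### The safety endpoint is meant to describe overall safety but admits only treatment-related events, so device-caused worsening attributed to the disease may go uncounted

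*Protocol*

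**What the plan says.** All of the relevant text is in the protocol.

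- **Objective** (Section 1, Study Objectives): "Establish a safety profile for both the procedure and the VibratoSleeve TUS for the treatment DFU". It sets no limit on relatedness.
- **Safety Endpoint** (Section 1): the purpose is "To evaluate the overall safety of the VibratoSleeve TUS device for the treatment of PAD", and the content is that "the Principal Investigator will undertake a detailed assessment of all procedure- and/or therapy-related adverse events". This is the only safety endpoint.
- **Design** (Section 1): "Prospective, single arm, open label clinical trial to evaluate the feasibility of TUS in the treatment of DFU".
- **Treatment** (Section 1): "Each subject will receive three levels of TUS treatment (low, medium, and high acoustic intensities, corresponding to different peak negative pressures". There is no sham or untreated period. Debridement and a wound assessment come before each session.
- **Number of Subjects** (Section 1): "Up to twelve subjects will be required for treatment and evaluation".
- **Table 1** (Section 3): adverse events are scheduled at screening and at all three treatment sessions, with no restriction to related events. Rutherford and University of Texas grading is scheduled at screening only. No visit follows the third session.

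**The concern.** The endpoint's purpose is broad and its content is narrow. A causality judgement decides which events enter it, and this design supports that judgement poorly. The Principal Investigator, who is the only named assessor, works unblinded. Nobody in the trial goes untreated, so there is no concurrent background rate against which to set a worsening ulcer or limb. The exclusion criteria on active ulcer infection, recent acute limb ischemia and planned revascularization show that the protocol itself expects such problems in this population. Harm from the device could look much the same.

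At stake is what a low count would mean. The synopsis says the data may support a 510(k) application. A short list of related events could reflect a benign device, or a habit of attributing worsening to the disease, and the endpoint as worded cannot tell the two apart.

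**Working it through.** **1. The plan's own figure.** The synopsis gives two inputs: 12 evaluable subjects, and "An estimated 50% of enrolled subjects may not satisfy all inclusion/exclusion criteria". Then 12 / (1 − 0.5) = 24, which matches the statement that "up to twenty-four subjects may have to be enrolled to generate twelve evaluable subjects". The protocol states no event rate, alpha or power, so there is nothing else to reproduce.

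**2. Scope, set side by side.**

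| Place | Events covered |
|---|---|
| Study Objectives | safety profile, no relatedness limit |
| Safety Endpoint, purpose | overall safety, no relatedness limit |
| Safety Endpoint, content | related events only |
| Table 1, collection | all adverse events, four visits |

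Only the third row applies the filter. The objective above it and the data collection below it are both wider.

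**3. What 12 subjects can show.** With 0 of 12 subjects having a counted event, the exact one-sided 95% upper bound is 1 − 0.05^(1/12) = 22.1%. The upper end of the two-sided 95% interval is 1 − 0.025^(1/12) = 26.5%. These bounds apply to the rate of events that pass the filter. If only a share s of device-caused events is judged related, the one-sided bound on the true rate becomes 22.1% / s, for example 22.1 / 0.5 = 44.2% at s = 0.5.

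**4. Effect of the filter (assumed rates, not from the documents).** Let p be the true proportion of subjects with device-caused worsening and s the chance that such an event is judged related. With subjects independent, the chance that at least one of 12 enters the endpoint is 1 − (1 − p·s)^12.

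| p | s = 1 (all events count) | s = 0.5 | s = 0.25 |
|---|---|---|---|
| 10% | 72% | 46% | 26% |
| 20% | 93% | 72% | 46% |
| 30% | 99% | 86% | 61% |

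For example, with p = 10% and s = 0.5, 1 − (1 − 0.05)^12 = 46%. Over this grid the range is 26% to 99%. At s = 0 the chance is 0%. Counting all events corresponds to s = 1, because no device-caused event can then be filtered out.

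**The case against.** The case on the other side has several parts.

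- **The events are not lost.** Table 1 collects adverse events without regard to relatedness, and the objective is unrestricted. This stands. A reader might infer that worsening attributed to the disease vanishes from the safety data. The documents do not support that, because such an event leaves the endpoint but stays on record.
- **Tabulation belongs to the statistical analysis plan.** True of table layouts, and the absence of tables is not the point here. The endpoint's scope is fixed in the protocol, and it is narrower than its stated purpose.
- **The sentence may describe closer scrutiny of related events, on top of routine reporting.** Possible, but it is the whole content of the only safety endpoint.
- **The text does not say who decides relatedness.** Correct. That the Principal Investigator does so is a natural inference, not a statement.
- **Individual attribution is not groundless.** This also stands. Timing, the device's position on the calf, the wound assessment before each session, and repeated ABI/TBI, TcPO₂ and perfusion measurements all help. It would be too strong to say that the investigator has no basis for judgement. The basis is imperfect, and it is weaker because formal ulcer and limb grading is not scheduled again after screening.
- **Comparing events by intensity level would not settle causality.** Agreed. The document shown states no order of levels, so level may be confounded with time and cumulative exposure. Sessions are at least a week apart, so windows vary, and none of the scheduled visits follows the third session.
- **This is a small pilot without hypotheses.** That limits the consequences, but it does not explain why the endpoint should be narrower than the data collected.

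**Conclusion.** The point holds as a defect in the endpoint's wording that should be corrected before results are reported. An endpoint meant to describe overall safety depends on a relatedness judgement made without blinding and without a comparison group. Device-caused ulcer or limb worsening may therefore fall outside it.

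The size cannot be derived from the documents. The illustration assumes true rates of 10% to 30%, attribution shares of 25% to 100%, and independent subjects. It shows the direction of the loss and its possible extent, and it is not an estimate. Nothing here shows that events will in fact be misattributed, and no stated figure is wrong.

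The endpoint's reference to PAD where the objective names DFU is editorial. The inclusion criteria require both conditions, so the label changes neither who is assessed nor what is counted.

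**What to change.** Reword the Safety Endpoint along these lines: all adverse events from the start of the first treatment session, whatever their relatedness, with the relatedness judgement reported for each event as an attribute and not used as a condition of entry. List adverse events from screening to first treatment separately. Table 1 allows the first session on the day of screening, so that period may be very short and should not be treated as a background rate.

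A listing by the level most recently received may be added as description only. It should state the order of levels and the length of observation after each, including that no visit is scheduled after the third session. The condition named in the endpoint can be aligned with the objective in the same edit.

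The cost is small: a wording change and one more column or listing, using events already collected at all four visits. The drawback is a higher headline count that mixes background disease events with any device effect. Related events remain visible through the attribute.

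### Does the protocol need a stated or randomised order of the three intensities to reach the conclusions it aims for?

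*Protocol*

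**What the plan says.** The Synopsis (Design) describes the trial as follows: "Prospective, single arm, open label clinical trial to evaluate the feasibility of TUS in the treatment of DFU". Under Treatment, "Each subject will receive three levels of TUS treatment (low, medium, and high acoustic intensities, corresponding to different peak negative pressures", and "Each of the three treatments will occur on separate dates, spaced at least one week apart". The same section gives the purpose: "This study is designed to address acute changes in perfusion with each of the three TUS treatments". Section 3 (Schedule of Events, Table 1) names its columns first, second and third treatment session, with no intensity attached, and adds: "All treatment visits will be completed within 3 months of the first treatment session".

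Under Statistical Hypothesis, the Synopsis plans no hypothesis test and then says, with later trials in view: "Information collected during the study may be used to support a 510(k) application as well as to select the endpoints and determine sample sizes". The study objectives are safety, initial evidence of efficacy during and immediately after treatment, and usability.

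The readable text has no rule linking intensity to session. The heading "2. STUDY FLOW CHART" is present, but the figure under it was not available for this review.

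**The concern.** Each subject is treated at all three intensities on different days, so the trial has the layout of a three-period, within-subject comparison, in which the order matters. If every subject goes through the levels in the same sequence, a difference between high and low is also a difference between two session numbers. The first and third sessions may be 14 days to 3 months apart (two gaps of at least 7 days, all within 3 months of the first). Each session also follows debridement. A different acute response at a later session could therefore reflect the course of the ulcer, repeated debridement or carry-over as well as intensity. If staff chose the order case by case, selection would take the place of session.

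The order is fixed once the sessions have been delivered, so a later analysis plan could not restore the separation. The results may also support a 510(k) application and the planning of future trials. If levels were compared for those purposes under one common order, the difference could not be attributed to intensity.

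**Working it through.** **The plan's own figure.** The only sample-size arithmetic in the Protocol is the enrolment figure: 12 / (1 − 0.50) = 24, as stated. The point does not depend on it.

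**Inputs.** Up to 12 treated subjects (Synopsis, Number of Subjects); 3 sessions and 3 levels, one level per session (Synopsis, Treatment; Table 1). The Protocol gives no SD or drift, so drift sizes below are assumptions, in SD units of the within-session change.

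**Aliasing.** Observations: 12 × 3 = 36. Parameters: 12 subjects + 2 session contrasts + 2 level contrasts = 16.

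| Order of levels | Rank | Level df free of session | Residual df |
|---|---|---|---|
| One common order | 14 of 16 | 0 | 36 − 14 = 22 |
| Low-medium-high in half, the reverse in half | 15 of 16 | 1 | 36 − 15 = 21 |
| Six orders, 2 subjects each | 16 of 16 | 2 | 36 − 16 = 20 |

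Under one common order, subject and session alone already give rank 14. Nothing is left for level, whatever the number of subjects.

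**Precision with balanced orders.** SE(high − low) = √(2/12) = 0.408 within-subject SD, with or without session in the model. Including session costs 22 − 20 = 2 residual df.

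**Bias from session effects.** Take an order of low, medium, high and no true level effect.

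- A shift at a session that moves pre and post values equally cancels from the within-session change. The bias in that change is 0, even in fixed order.
- A drift of d per session in the acute response itself does not cancel. High is given two sessions after low, so the bias is 2d: 2 × 0.10 = 0.20, 2 × 0.25 = 0.50, 2 × 0.50 = 1.00 SD.
- With six balanced orders, each level falls in each session for one third of subjects. The drift averages out and the bias is 0.00.

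**What balanced orders do not remove.** Suppose carry-over into the next session is 0, 0.25 and 0.50 SD after low, medium and high. Over the six orders, each level comes first in a third of subjects and follows each of the other two levels in a third.

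- Mean carry-over received by high: (0 + 0 + 0.25) / 3 = 0.083.
- Mean received by low: (0 + 0.25 + 0.50) / 3 = 0.250.
- Bias in high minus low: 0.083 − 0.250 = −0.17 SD.

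Carry-over of equal size after every level cancels.

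**Fewer than twelve treated.** In randomised blocks of six, 6 to 11 subjects keep full rank, and the SE is at most 2.6% above √(2/n) (worst at n = 9). With three subjects it can be 34% above. With two, 9 of the 15 possible pairs of different orders lose rank.

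**The case for a change.** The strongest case for a change is that the order is trial conduct and is not normally left to an analysis plan. Staff must pick a level at each session, and the readable text gives them no rule. Writing the order down would cost one sentence, or a 12-line list if it were randomised, with no extra subjects or visits. Results will naturally be shown by level, and readers will compare them even without a test. An acute response that changes over the sessions is plausible, given repeated debridement and an evolving wound.

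Much of this stands. The aliasing under a common order is complete, and no later model can undo it. A statement of how levels are assigned is worth having if the flow chart does not give it.

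It does not carry the point to a change, for four reasons.

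- A flow chart for three sessions at three intensities is a natural place to show the sequence, and its content is unknown here. Table 1 is a data-collection table, so its silence on level is weak evidence.
- The harm needs a common order, which no text states, and a comparison between levels, which no objective calls for. The planning uses named are endpoint selection and sample size. Choosing an intensity is not among them.
- The sizes of 0.20 to 1.00 SD are twice an assumed drift in the acute response. The Protocol gives no figure for such a drift, and a shift in the session level alone produces none.
- Randomised order is not a full remedy: it deals with session drift but leaves carry-over that differs by level. Some subjects would also not start at the lowest level, which is a device-safety judgement for the sponsor. A fixed order is acceptable provided differences between levels are not attributed to intensity.

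**Conclusion.** No change to the plan follows. The calculation is correct: one common order gives rank 14 of 16, and any difference between levels in acute response would then be inseparable from session. But neither the common order nor the comparison is in the plan, and the place most likely to show the order could not be read. The acute change at each session keeps its meaning under any order, as do the safety and usability descriptions, so following the text still supports the conclusions the Protocol sets out to draw.

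Two things remain, both minor. One is a detail that the sponsor can confirm from the flow chart, or write down if it is not there. The other is a trade-off between fixed and randomised order, where balancing has no SE penalty at 12 subjects (0.408 SD) but leaves a bias of −0.17 SD under the carry-over assumed above. No order is proposed here on clinical grounds. Should the order prove to be fixed, analysts would sensibly describe results by level without attributing differences to intensity.

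This rests on two assumptions: that the levels are not compared in order to claim dose response or to choose an intensity, and that the stated aim of acute change at each treatment governs how the results are read.
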